10.3.3. Safety Analysis

a. Analysis of Adverse Events

Study Title: Maternal Fetal Device Performance Testing During Antepartum Singleton Monitoring

Study Number: SA-000072

Version Number: 2.0

Version Date: 23SEP2024

GE HealthCare

When applicable, AE will be listed per subject, summarized with counts and percentages of events, and summarized with counts and percentages of subjects with events.

When applicable, the incidence of AE will be computed by the number of AEs divided by the total enrolled subjects. The AEs will be categorized into different groups and reported using summary tables and listings.

b. Analysis of Device Deficiencies/Complaints

If applicable, the device deficiencies will be reported using summary tables and listings. The incidence of device deficiencies will be computed by the number of device deficiencies divided by their corresponding totals.

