3.2.3. Safety Endpoints

The safety endpoints of this study are type and number of AEs, SAEs, and device issues.

Study Title: Maternal Fetal Device Performance Testing During Antepartum Singleton Monitoring

Study Number: SA-000072

Version Number: 2.0

Version Date: 23SEP2024

GE HealthCare

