4.6. Recruiting and Screening

Subjects will be recruited for potential enrollment in this study according to the standard procedures of the investigational site, unless otherwise specified by the Sponsor in this study protocol. All participation will be voluntary.

Following recruitment and screening, a subject will be considered enrolled (the point of enrollment) once the ICF is signed and dated. Once enrolled, the subject is assigned a unique subject number which will not contain information that could identify the subject (such as subject date of birth). Unique subject number will be used to label electronic Case report form (eCRF (MediData) data for the subject throughout her participation in the study.

Based on the vulnerability of subjects at the time of study eligibility, subjects may be consented prior to meeting all inclusion/exclusion criteria. Subjects must go on to meet all inclusion/exclusion criteria prior to conducting study procedures, any subject who does not go on to meet all inclusion/exclusion criteria will be considered a screen failure and withdrawn from the study. The number of screen failures will be included in the screening and enrollment log.

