5.3. Follow-up

This study does not require follow-ups. The Sponsor is responsible for assuring that the study device fulfills the biomedical safety and standards requirements of the investigational site.

No follow-up will be conducted after the subject's participation has ended. The subject will be followed for AEs from the time the research device is connected to the subject. In addition, all AEs, including those involving delayed reactions, will be followed through to resolution.

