8.3. Documentation of Adverse Events

All adverse events (AE), including all serious adverse events (SAE), are required to be collected, investigated, and documented. AEs will be collected from subject enrollment period, and during scanning period for each visit. All AEs will be followed through to their resolution. Documentation will include:

- Description of Event
- Date of onset
- Date of resolution unless resolution does not occur during study reporting period. In the instance that resolution does not occur, the status of the AE will be documented (not resolved/recovered or resolving/recovering)
- Severity (mild, moderate, or severe)
 - *Mild:* Symptom(s) barely noticeable to the subject or does not make the subject uncomfortable. The AE does not influence performance or functioning. Prescription drugs are not ordinarily needed for relief of symptom(s).
 - *Moderate:* Symptom(s) of a sufficient severity to make the subject uncomfortable. Performance of daily activities is influenced. Treatment of symptom(s) may be needed.
 - *Severe:* Symptom(s) of a sufficient severity to cause the subject severe discomfort. Treatment for symptom(s) may be given.
- Serious (yes/no)
- Causal relationship to investigational or comparator medical device? (not related, possible, probable, or causal relationship)
 - *Not related:* Relationship to the device, comparator or procedures can be excluded when:
 - the event has no temporal relationship with the use of the investigational device, or the procedures related to application of the investigational device;
 - the serious adverse event does not follow a known response pattern to the medical device (if the response pattern is previously known) and is biologically implausible;
 - the discontinuation of medical device application or the reduction of the level of activation/exposure - when clinically feasible - and reintroduction of its use (or increase of the level of activation/exposure), do not impact on the serious adverse event;
 - the event involves a body-site or an organ that cannot be affected by the device or procedure;
 - the serious adverse event can be attributed to another cause (e.g., an underlying or concurrent illness/clinical condition, an effect of another device, drug, treatment or other risk factors);
 - the event does not depend on a false result given by the investigational device used for diagnosis, when applicable;

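### The AE incidence in section 10.3.3 is an event rate per consented woman rather than an incidence among monitored women, and sections 5.3 and 8.3 start AE collection at different points

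*Combined protocol and SAP*

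**What the plan says.** Section 10.3.3 gives an explicit formula: "the incidence of AE will be computed by the number of AEs divided by the total enrolled subjects". Just before it, the same section plans a listing of AEs for each woman and has AEs "summarized with counts and percentages of subjects with events". It does not say which women form the base of that percentage. Section 10.3.1 has the sample size shown with categorical summaries, again without naming a safety population. No safety analysis set is defined.

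On enrolment, section 4.6 says that "a subject will be considered enrolled (the point of enrollment) once the ICF is signed and dated". Sections 4.3 and 4.6 allow consent before the entry criteria are all met, and section 4.6 adds that "any subject who does not go on to meet all inclusion/exclusion criteria will be considered a screen failure and withdrawn from the study". Section 4.8 foresees a further group, women enrolled but never given the study procedure, and allows their replacement.

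On the AE window, section 5.3 says: "The subject will be followed for AEs from the time the research device is connected to the subject". Section 8.3 says: "AEs will be collected from subject enrollment period, and during scanning period for each visit". Section 6.3 has any AE occurring during the study recorded. The endpoint that depends on these rules is in section 3.2.3: "The safety endpoints of this study are type and number of AEs, SAEs, and device issues".

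**The concern.** A reader of the study report will take AE incidence to mean the share of monitored women who had an AE. The formula departs from that in two ways. Its denominator can include women who were never connected to either monitor, and its numerator counts each event, so several AEs in one woman each add to the figure.

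The window is a separate problem. The safety endpoint is itself a count of AEs. If one section starts the count at device connection and another at enrolment, two analysts following the protocol could report different totals from the same study. An AE between consent and connection that a site did not record, because it followed section 5.3, cannot be recovered later. The results are meant for FDA 510(k) and CE-mark submissions, so the reported safety figures should have one meaning.

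**Working it through.** **No figure to reproduce.** The documents state no AE rate, AE count or screen-failure rate, and the sample size is not derived from any safety quantity. All AE counts and all numbers of unconnected women below are assumptions.

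**Inputs from the documents.** At least 30 women, 10 completed in each of three gestational-age groups (section 4.3): 3 × 10 = 30. Enrolled means consent form signed (section 4.6). Screen failures and women who never start the procedure are both foreseen (sections 4.6 and 4.8).

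**The two measures.**
- A (plan) = AEs / women enrolled
- B (incidence among monitored women) = women with at least one AE / women connected

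If all AEs occur in connected women, A/B = (AEs per affected woman) × (connected / enrolled). The first factor is at least 1 and the second at most 1, so they pull in opposite directions.

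**Denominator alone, AEs counted from connection (section 5.3), 30 women connected.**

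| Enrolled but not connected | Connected / enrolled |
|---|---|
| 0 | 30/30 = 1.00 |
| 3 | 30/33 = 0.91 |
| 5 | 30/35 = 0.86 |
| 10 | 30/40 = 0.75 |

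If 5 of the 10 extra women were connected but did not complete monitoring, the factor is 35/40 = 0.875.

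**Numerator alone.** Three AEs in one woman, 30 enrolled and all connected: A = 3/30 = 10%; B = 1/30 = 3.3%.

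**Both together: 40 enrolled, 30 connected, 3 AEs after connection.** A = 3/40 = 7.5% in every row.

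| Women with an AE | B | A/B |
|---|---|---|
| 3 | 3/30 = 10% | 1 × 0.75 = 0.75 |
| 2 | 2/30 = 6.7% | 1.5 × 0.75 = 1.125 |
| 1 | 1/30 = 3.3% | 3 × 0.75 = 2.25 |

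The plan's figure can therefore fall below or above the incidence among monitored women.

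**Window: 3 AEs after connection and 0, 1 or 2 between consent and connection.** The count is 3 under section 5.3, and 3, 4 or 5 under section 8.3. Formula A applied to the section 8.3 counts gives:

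| AEs before connection | AEs counted | 30 enrolled | 40 enrolled |
|---|---|---|---|
| 0 | 3 | 10% | 7.5% |
| 1 | 4 | 13.3% | 10% |
| 2 | 5 | 16.7% | 12.5% |

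Under section 8.3 an unconnected woman can contribute an event as well as a place in the denominator. The simple dilution factor then no longer applies, although the result is still not a rate among monitored women.

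**The case against.** The strongest reply is that section 10.3.3 already plans the woman-level summary, together with per-woman listings, and that section 10.3.1 shows the sample size beside each percentage. This is right as far as it goes. A reader might infer that the plan has no count of women with AEs, and the text does not support that. What is missing is the population behind the percentage, and the label *incidence* stays on the event ratio.

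Second, AEs per enrolled woman is an explicit, reproducible formula, and renaming it an event rate would settle much of the numerator point. That stands, and the fix adopts it.

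Third, section 4.5 uses enrolment for women who meet the criteria, and section 4.6 withdraws screen failures. But section 4.6 also defines the point of enrolment explicitly as the signed consent form, and nothing takes withdrawn women out of the denominator. The fair statement is that the denominator can include them.

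Fourth, section 6.3 and the documentation rules in section 8.3 lean towards collection from enrolment, and the connection start appears only in the Follow-up section. Nor does the sentence in section 5.3 concern only follow-up to resolution, since that section covers resolution separately. The conflict remains, though the balance of the text is not even.

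Finally, an exposed-women rate could be rebuilt from the per-woman listings and the log: "The number of screen failures will be included in the screening and enrollment log". That is true for AEs that were recorded, but the plan does not call for it.

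**Conclusion.** The point holds as a minor one. The stated formula does not give an incidence among monitored women, no population is named for the planned percentages, and the AE start point differs between sections 5.3 and 8.3 for an endpoint that is a count of AEs.

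Two stronger readings are not supported. One is that the formula always understates AE frequency. Dilution by connected/enrolled follows only if AEs are counted from connection, and repeat events push the other way; in the illustration A/B runs from 0.75 to 2.25. The other is that the rate could be halved because section 4.3 allows up to 60 women with 30 completed. That requires the maximum of 60 to count every consented woman and every woman beyond 30 to be unconnected, and section 4.3 says neither.

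The practical size is probably small. Participation lasts about 90 minutes (section 4.2), the entry criteria are simple, and there is no safety hypothesis. The actual size depends on screen-failure and AE rates that the documents do not give. The primary non-inferiority conclusion on success rate is unaffected.

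**What to change.** - Define the safety set as all women connected to at least one study device.
- Report incidence as women with at least one AE over that set, and use the same denominator for the planned percentages of women with events.
- Count a woman once in the per-woman rate if she takes part in more than one gestational-age group, which section 4.5.2 allows.
- Relabel AEs per woman as an event rate, and show event counts separately.
- List AEs in enrolled but unconnected women separately.
- Reconcile the AE start point across sections 5.3, 6.3 and 8.3, so that one rule governs both collection and counting.

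The cost is minor wording and tabulation. The reported rate may go up because of the smaller denominator, or down because women replace events. Reconciling on an enrolment start would mean that sites record AEs from consent, which section 8.3 already appears to ask of them.

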10.3.4. Subgroup analysis

Analysis may also be performed for subgroups based on gestational age as an exploratory analysis.

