Eligibility Criteria:	
Inclusion criteria:
 
Subjects who meet all the following inclusion criteria may be enrolled:
 
1. Able and willing to provide written informed consent.2. Singleton pregnancy3. Aged 18+4. Greater than or equal to 22 0/7 weeks gestation5. Patient has none of the exclusion criteria.	
Exclusion criteria:
 
Subjects who meet any of the following exclusion criteria may not be enrolled:
 
1. Multiple pregnancy.2. Involvement in another clinical trial currently or previously in this pregnancy that, in the investigator's opinion, would affect the conduct of this study.3. Medical or obstetric problem that in investigator's opinion would make the patient incapable of taking part in the study.4. Inability to understand the consent information due to medical illness, diminished intellectual capacity, or insurmountable language barrier. 
[REDACTED]
 
[REDACTED]

Study Title: Maternal Fetal Device Performance Testing During Antepartum Singleton Monitoring

Study Number: SA-000072

Version Number: 2.0

Version Date: 23SEP2024

GE HealthCare

Sample Size and Sites:

This study is intended to be conducted at one United States site. Subjects will be divided into three groups based on gestational age groups.

Table 1: Target Enrollment Groups

Subject Gestational Age Groups	Target Enrollment
Group 1: 22 0/7 – 24 6/7 Weeks	10
Group 2: 25 0/7 – 31 6/7 Weeks	10
Group 3: ≥ 32 0/7 Weeks	10

[REDACTED] randomization schema will be provided by the sponsor within each gestational age group.

Sample Size and Site:

The sample size has not been derived from a statistically powered endpoint but has been determined based on a review of the literature, bench testing results and publicly available regulatory filings.

[REDACTED] The study is expected to last 4 months.

Study Duration:

[REDACTED] The study will be deemed completed following completion of data collection of the last enrolled subject.

Study Title: Maternal Fetal Device Performance Testing During Antepartum Singleton Monitoring

Study Number: SA-000072

Version Number: 2.0

Version Date: 23SEP2024

GE HealthCare

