3.2. Study Endpoints

3.2.1. Primary Endpoints

The primary endpoint of this study is collection of FHR data from 30 subjects undergoing routine monitoring during antenatal period to allow for analysis of the reliability of the two maternal fetal monitors.

Reliability will be measured in terms of success rate which is defined as percentage of time in which the device gives FHR reading during the study monitoring period. Non-inferiority of [REDACTED] with respect to Corometrics 259cx will be tested using a non-inferiority margin of -10%.

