4.3. Number of Subjects/Cases

The study includes a minimum of 30 subjects (with a maximum of 60 subjects), divided equally (10 subjects) in each gestational age group. Based on the vulnerability of subjects at the time of study eligibility, subjects may be consented prior to meeting all inclusion/exclusion criteria. Subjects must go on to meet all inclusion/exclusion criteria prior to conducting study procedures, any subject who does not go on to meet all inclusion/exclusion criteria will be considered a screen failure and will be withdrawn from the study. Subjects will be enrolled until the target numbers of 10 completed subjects in each gestational age groups are met: Group 1, 22 0/7 – 24 6/7 weeks, Group 2, 25 0/7 – 31 6/7 weeks and Group 3, \geq 32 0/7 weeks is achieved.

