10. STATISTICAL METHODS

10.1. Statistical Hypothesis

Non-inferiority of [REDACTED] with respect to Corometrics 259cx will be tested using the following primary hypothesis:

Reliability as measured by Success rate (SR) for FHR data:

$$H_0 = \text{Mean SR } [REDACTED] - \text{Mean SR (Corometrics 259cx US)} \leq -10\%$$

$$H_A = \text{Mean SR } [REDACTED] - \text{Mean SR (Corometrics 259cx US)} > -10\%$$

The test will be performed using two-sided 95% CI of the difference in Mean SR. If lower 95% CI of the difference is greater than -10%, non-inferiority will be concluded.

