10.2. Sample Size Determination

Minimum sample sizes are described in Section 4.7.

The sample size has not been derived from a statistically powered endpoint but has been determined based on a review of the literature, bench testing results and publicly available regulatory filings.

Based on those factors it has been concluded that 30 Corometrics and Lotus data sets would sufficiently confirm the intended use of the investigational maternal fetal monitor.

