10.3.2. Analysis of Primary Endpoint(s)

Fetal Heart Rate (FHR)

For each subject, the whole length of time when both Corometrics 259cx and [REDACTED] independently record data will be considered for statistical analysis. The reliability of the FHR data will be analyzed based on the following primary endpoint.

Success rate (SR) for FHR data:

To ensure that most of the epochs are available and evaluable, the individual SR, which measures the percentage of time that [REDACTED] or Corometrics Ultrasound (independently) generates a value for FHR, will be computed per subject (irrespective of the other device generating a value or not)). Overall SR across subjects will be summarized along with its 95% CI for each device.

$$SR(FHR)_i(\%) = \frac{a_i}{a_i + b_i} * 100$$

Where,

SR_i is the ith individual SR;

a_i is represents the number of sample points when the FHR is present (i.e. has a value other than 0) for the ith subject;

b_i is the number of sample points when the FHR is not present (i.e. the device is turned on but has a value of 0) for the ith subject;

From the start of the FHR trace, only a segment of 30 minutes duration will be considered for calculating the SR value. If the data length is greater than 30 minutes, the first 30 minutes of data will be considered for analysis. If either Corometrics or [REDACTED] has less than 30 minutes of recording, the data from both devices will be eliminated from the primary endpoint analysis but could be used for engineering development. Any gaps in the data due to pausing study procedures will be excluded from the 30-minute monitoring data that will be used for analysis. The difference in mean SR (Lotus – Corometrics 259cx) will be computed along with its two-sided 95% CI to test non-inferiority. If the lower 95% CI is greater than -10%, non-inferiority will be concluded.

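### The only verdict is one pooled difference in success rate, so a deficit beyond the margin in one gestational-age group can pass, and no results by group are required

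*Combined protocol and SAP*

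**What the plan says.** Section 4.3 sets the quotas: "Subjects will be enrolled until the target numbers of 10 completed subjects in each gestational age groups are met". The groups run from 22 0/7 to 24 6/7 weeks, from 25 0/7 to 31 6/7 weeks, and from 32 0/7 weeks on. The synopsis, under Sample Size and Sites, adds that a "randomization schema will be provided by the sponsor within each gestational age group".

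The decision rule does not use the groups. Section 10.1 states: "The test will be performed using two-sided 95% CI of the difference in Mean SR", and then: "If lower 95% CI of the difference is greater than -10%, non-inferiority will be concluded". Section 10.3.2 repeats this for the primary analysis: the difference in mean SR "will be computed along with its two-sided 95% CI to test non-inferiority". Neither section has a group term, a criterion by group or a table by group.

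Gestational age enters the analysis only in Section 10.3.4: "Analysis may also be performed for subgroups based on gestational age as an exploratory analysis". Section 10.2 says that the sample size does not come from a powered endpoint.

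**The concern.** The design treats gestational age as important enough to fix quotas and to randomise within groups, but the analysis may ignore it. With equal groups, each carries one third of the weight in the pooled mean. A device that falls short by more than the 10-point margin in one group can therefore meet the criterion on the strength of the other two.

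The optional wording adds a second problem. A group table that may or may not be produced can be shown or left out once its content is known. The data are meant for regulatory submissions, and a reader of the result would have no assurance of seeing whether the three groups agree.

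**Working it through.** **Inputs from the documents.** Margin -10, read as percentage points of SR (Sections 3.2.1 and 10.1). Lower limit of a two-sided 95% CI (10.1). Ten completed subjects in each of three groups, 30 in all (4.3, 10.2). Each subject is monitored on both devices (4.8, 5.1). The plan states no power, SD or expected difference, so it has no figure of its own to reproduce.

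**Assumptions.** The CI is paired (the plan does not name the method). Within-subject differences are normal with the same SD in each group, from 5 to 20 points. The true difference is 0 in two groups and negative in the third. All 30 data sets are independent, although Section 4.5.2 lets a woman join more than one group.

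**Dilution.** The pooled mean is (deficit + 0 + 0)/3. Deficits of -12, -15, -20 and -25 become -4.0, -5.0, -6.7 and -8.3, all inside the margin.

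**Planned rule.** Pass if mean - t(29) × s/√30 > -10, with t(29) = 2.045. With no group term, s includes the spread between groups. For a -15 deficit, s² is about [27 × SD² + 10 × (-15 + 5)² + 20 × (0 + 5)²]/29.
- SD 10: s² = (2,700 + 1,500)/29 = 144.8 and s = 12.03. Lower limit = -5 - 2.045 × 12.03/5.477 = -9.49, which passes.
- SD 15: s² = (6,075 + 1,500)/29 = 261.2 and s = 16.16. Lower limit = -5 - 6.03 = -11.03, which fails on average but passes in a sizeable minority of trials.

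**Same mean with group as a factor.** The error is the within-group SD, with t(27) = 2.052.
- SD 10: -5 - 2.052 × 10/5.477 = -8.75.
- SD 15: -5 - 2.052 × 15/5.477 = -10.62.

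The estimate does not move; only the interval narrows.

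**Simulated chance (%) of concluding non-inferiority** (at least 100,000 trials per cell):

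| Deficit in one group | Pooled CI | SD 5 | SD 8 | SD 10 | SD 15 | SD 20 |
|---|---|---|---|---|---|---|
| -12 | no group term | 100 | 94 | 82 | 51 | 33 |
| -15 | no group term | 96 | 75 | 59 | 34 | 22 |
| -15 | group as factor | >99 | 91 | 75 | 42 | 26 |
| -20 | no group term | 24 | 20 | 17 | 13 | 10 |
| -20 | group as factor | 94 | 60 | 42 | 22 | 14 |
| -25 | no group term | 0.1 | 0.8 | 1.6 | 2.9 | 3.5 |
| -25 | group as factor | 42 | 20 | 14 | 8.5 | 6.5 |

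**What a group table would show.** With a -15 deficit, among trials that pass with no group term, the affected group's estimate lies below -10 in about 97%, 91%, 67% and 47% at SD 8, 10, 15 and 20. With group as a factor it is 93% at SD 10 and 73% at SD 15.

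The share of all trials that pass without such an estimate is then:
- SD 10: 59% × 9% = 5% with no group term, and 75% × 7% = 5% with the factor.
- SD 15: 34% × 33% = 11%, and 42% × 27% = 11%.

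The extra passes that the factor creates are thus almost all ones in which the table would show an estimate beyond the margin.

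**Precision of a group estimate.** Half-width = t(9) × SD/√10 with t(9) = 2.262: 2.262 × 10/3.162 = 7.2 points at SD 10, and 10.7 at SD 15.

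**The case against.** The hypothesis is openly about an overall mean. In the -15 scenario the true pooled difference is -5, so a pass is a correct answer to the question that Section 10.1 asks, not a type I error. Quotas can serve representativeness without creating a claim for each group. Exploratory subgroups are conventional at 10 per group, where a full CI criterion would have only 47% power per group at SD 15 even for an equal device. All of this stands, and it is why no formal test by group is asked for. It does not justify leaving the descriptive results optional.

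A reader might infer more than the documents support:

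- *That the 22 to 24 week group is the likely point of failure.* The background sections link signal loss to fetal and maternal movement and never say that the fetal heart rate is harder to obtain at early gestation. Poor signal on both devices would also leave the difference unchanged. The dilution applies equally to any group.
- *That a pass would be claimed for all women from 22 weeks.* The intended-use text is blacked out, so this cannot be checked.
- *That a group table would nearly always expose the deficit.* Among passing trials it does so at SD 8 or 10, in about two thirds at SD 15, and in fewer than half at SD 20.
- *That a group estimate below -10 should by itself limit the claim.* For a truly equal device, at least one of the three estimates falls below -10 in about 5% of trials at SD 15 and 16% at SD 20. A fixed rule is not warranted.

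**Conclusion.** The concern holds as a gap in reporting and in the error term. The pooled rule can conclude non-inferiority when one gestational-age group is beyond the margin, and the plan requires nothing that would show it. At a 15-point deficit the chance runs from about 75% at SD 8 to 22% at SD 20. The rule as planned mostly stops larger failures: 10 to 24% pass at 20 points and under 4% at 25.

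These rates rest on assumed deficits and SDs, a paired CI, normal differences, equal SD across groups and independent data sets. The deficit is a scenario, not a forecast.

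A reader might also infer that putting gestational-age group into the model cures the problem. It does not. It gives the right error term for fixed quotas, but it makes a pooled pass more likely when the groups differ, including at -20 and -25.

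**What to change.** 1. In Section 10.3.4, make the gestational-age analysis mandatory (will instead of may). Report the mean paired SR difference with a two-sided 95% CI for each of the three groups next to the pooled result, labelled descriptive.
2. In Sections 10.1 and 10.3.2, compute the pooled difference and its CI with gestational-age group as a factor on the paired differences. Quotas and randomisation are by group, and without the factor the error term wrongly includes the spread between groups. A group main effect in a subject-level mixed model would not do this, because it leaves the within-subject device contrast unchanged.
3. State in the plan that the factor narrows the CI and so makes a pooled pass more likely when groups differ (59% to 75% at SD 10 in the -15 scenario), and that it is therefore always reported with the group table. If only one change is made, it should be the table.
4. Keep the pooled test as the only formal test.

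The cost is a change of wording, one table and two degrees of freedom, with no new data. The group intervals will be wide (about ±7.2 points at SD 10 and ±10.7 at SD 15), and an unfavourable group estimate would be visible. Both changes should be made before any data are seen.
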